7.1 Use of Concomitant Medications

The use of the medications listed below are not exclusionary in and of itself; rather their use will be evaluated by the Principal Investigator, treating physician, and/or a pharmacist on a case-by-case basis.

- Participants receiving chemotherapy or immunotherapy should be receiving a regimen that will allow them to schedule their Ketamine session (Day 0/Visit 4) at least 5-7 days after the end of a treatment cycle and at least 5-7 days before the beginning of the next treatment cycle.
- NMDA receptor antagonists (e.g., memantine, amantadine, dextromethorphan, methadone)
- Chronic benzodiazepine use can be continued as a stable, scheduled regimen, except for the morning of the ketamine administration visit (Day 0/Visit 4)
- Chronic antidepressant and serotonergic supplement use can be continued as a stable, scheduled regimen
- Drugs that may increase the risk of hypertension and tachycardia (e.g., levothyroxine, monoamine oxidase inhibitors [MAOIs]) [104, 105]
- Drugs that may increase the risk of seizures (e.g., metrizamide, theophylline and bupropion)
- Drugs that may increase the risk of neuromuscular blockade (e.g., atracurium and tubocurarine)
- Inhibitors or inducers of CYP 2B6, 2C9, 3A4 (e.g., clopidogrel and ticlopidine)**
 **Cytochrome P450 Inhibitors and Inducers
 - After careful consideration, participants may qualify for the trial if they are taking medications that are inhibitors or inducers of CYP 2B6, 2C9, or 3A4. Drug-drug interactions will be assessed against the evidence for the strength of the interaction using peer-reviewed literature (e.g., Flockhart Table https://drug-interactions.medicine.iu.edu/MainTable.aspx), and the participant's medical status, co-morbidities, and concomitant medications will be taken into consideration.

7.2 Dietary Restrictions

Participants will be asked to adhere to the following guidelines before receiving their ketamine dose (on Day 0/Visit 4):

- Consume no more than a modest quantity (e.g., 1 cup) of caffeine or xanthinecontaining products (e.g., coffee or tea)
- Abstain from nicotine for at least 3 hours before ketamine administration
- Abstain from alcohol and any other non-prescribed substances for 24 hours before receiving ketamine

Pilot Study - Ketamine Page 36 of 55

 If cannabis products are used regularly, participants will be asked to maintain their regular amount but will be asked not to use cannabis within 24 hours prior to receiving ketamine.

7.3 Prohibited Medications

The medications below may not be used during the study. If participants require these medications, they will be taken off-study (except for when anxiolytics as rescue medications ar used during the ketamine medication visit on Day 0/Visit 4).

- Anxiolytics, as needed
- Lithium

7.4 Evaluation of Safety

The safety parameters for this study include all laboratory tests, physical findings, and spontaneous reports of adverse events reported to the investigator by participants.

Safety will be assessed according to the NCI CTCAE version 5.0.

Safety analyses will be performed for all participants who receive ketamine treatment in the trial (V2).

8 Safety Parameters

8.1 Definitions

8.1.1 Adverse Event (AE)

Adverse event means any untoward medical occurrence associated with the use of an intervention in humans, whether or not considered intervention-related (21 CFR 312.32 (a)).

8.1.2 Serious Adverse Event (SAE)

An adverse event is considered *serious* if, in the view of either the investigator or Sponsor-Investigator, it results in any of the following outcomes:

- Death
- Life-threatening adverse event
 - An adverse event is considered life-threatening if, in the view of either the investigator or Sponsor-Investigator, its occurrence places the participant at immediate risk of death. It does not include an adverse event that, had it occurred in a more severe form, might have caused death.
- Inpatient hospitalization or prolongation of existing hospitalization
- A persistent or significant incapacity or substantial disruption of the ability to conduct normal life function
- Congenital anomaly/birth defect

Pilot Study - Ketamine Page 37 of 55

Important medical events that may not result in death, are life-threatening, or require hospitalization may be considered serious when, based upon appropriate medical judgment, they may jeopardize the participant and may require medical or surgical intervention to prevent one of the outcomes listed in this definition. Examples of such medical events include allergic bronchospasm requiring intensive treatment in an emergency room or at home, blood dyscrasias or convulsions that do not result in inpatient hospitalization, or the development of drug dependency or drug abuse.

8.1.3 Unanticipated Problem (UP)

An unanticipated problem (UP) is any incident, experience, or outcome that meets all of the following criteria:

- unexpected (in terms of nature, severity, or frequency) given (a) the research procedures are described in the protocol-related documents, such as the IRBapproved research protocol and informed consent document; and (b) the characteristics of the subject population being studied;
- 2) related or possibly related to participation in the research; and
- suggests that the research places subjects or others at a greater risk of harm (including physical, psychological, economic, or social harm) related to the research than was previously known or recognized.

Only a small subset of adverse events occurring in human subjects participating in research will meet these three criteria for an unanticipated problem. Furthermore, there are other types of incidents, experiences, and outcomes that occur during the conduct of human subjects research that represent unanticipated problems but are not considered adverse events. For example, some unanticipated problems involve social or economic harm instead of the physical or psychological harm associated with adverse events. In other cases, unanticipated problems place subjects or others at increased risk of harm, but no harm occurs.

8.2 Classification of Adverse Events

8.2.1 Severity

Adverse events are graded according to the National Cancer Institute Common Terminology Criteria for Adverse Events (CTCAE) version 5.0.

8.2.2 Attribution

Following expert guidance in adverse event assessment [106] and reporting [107], all serious adverse events (SAEs) must have their relationship to study intervention assessed by the clinician who examines and evaluates the participant based on temporal relationship and his/her clinical judgment. However, relatedness to study intervention will not be assessed for non-serious adverse events (AEs). The degree of certainty about causality for SAEs will be graded using the categories below. In a clinical trial, the study product must always be suspect.

- **Related** The SAE is known to occur with the study intervention, there is a reasonable possibility that the study intervention caused the SAE, or there is a temporal relationship between the study intervention and event. Reasonable possibility means that there is evidence to suggest a causal relationship between the study intervention and the SAE. In summary, the SAE is more likely related to the study intervention than to other causes.
- **Unrelated** There is not a reasonable possibility that the administration of the study intervention caused the event, there is no temporal relationship between the study

Pilot Study - Ketamine Page 38 of 55

intervention and event onset, or an alternate etiology has been established. In summary, the SAE is more likely related to other causes than to the study intervention.

• **Unknown** – It is equally likely that the SAE is related to the study intervention as to other causes.

8.2.3 Expectedness

An adverse event is considered unexpected if the nature, severity, or frequency of the event is not listed in the study protocol, product inserts, investigator brochure or informed consent document.

8.3 Recording of Adverse Events

Refer to the Data Safety Monitoring Plan, located in Appendix 2.

8.4 Expedited Reporting

8.4.1 Reporting to the HDFCCC Data and Safety Monitoring Committee

If a death occurs during the treatment phase of the study or within 30 days after the last administration of the study drug(s) and it is determined to be related either to the study drug(s) or to a study procedure, the UCSF PI or his/her designee must notify the DSMC Chair (or qualified alternate) within 1 business day of knowledge of the event. The contact may be by phone or e-mail.

8.4.2 Reporting to Institutional Review Board

The UCSF PI must report events to the IRB according to institutional guidelines.

8.4.3 Expedited Reporting to the FDA

If the study is being conducted under an IND, the Sponsor (or the Sponsor-Investigator) is responsible for determining whether or not the suspected adverse reaction meets the criteria for expedited reporting in accordance with federal regulations (21 CFR §312.32).

The Sponsor (or Sponsor-Investigator) must report in an IND safety report any suspected adverse reaction that is both serious and unexpected. The Sponsor needs to ensure that the event meets all three definitions:

- Suspected adverse reaction
- Unexpected
- Serious

If the adverse event does not meet all three of the definitions, it should not be submitted as an expedited IND safety report.

The timeline for submitting an IND safety report to FDA is no later than **15 calendar days** after the Investigator determines that the suspected adverse reaction qualifies for reporting (21 CFR 312.32(c)(1)).

Any unexpected fatal or life-threatening suspected adverse reaction will be reported to FDA no later than **7 calendar days** after the Investigator's initial receipt of the information (21 CFR 312.32(c)(2)).

Any relevant additional information that pertains to a previously submitted IND safety report will be submitted to FDA as a Follow-up IND Safety Report without delay, as soon as the information is available (21 CFR 312.32(d)(2)).

Pilot Study - Ketamine Page 39 of 55

8.5 Follow-up of Adverse Events

All participants who experience adverse events will be followed with appropriate medical management until resolved or stabilized, as determined by the investigator. For selected adverse events for which administration of the study drug/intervention was stopped, a re-challenge of the subject with the study drug/intervention may be conducted if considered both safe and ethical by the investigator.

8.6 Adverse Events Monitoring

Refer to the Data Safety Monitoring Plan, located in Appendix 2.

9 Statistical Considerations and Evaluation of Results

9.1 Sample Size Considerations

9.1.1 Sample Size and Power Estimate

No formal power analysis was conducted, and no formal tests of efficacy will be conducted. This N=12 pilot study has a sample size sufficient for assessing the feasibility and preliminary safety of a novel behavioral-pharmaceutical intervention, at two different dose levels and routes of administration of the study drug.

If the 0.5mg/kg PO dose of ketamine is well-tolerated (i.e., zero treatment-related SAEs) and demonstrates mean clinical improvement in demoralization assessed by DS-II that endures beyond 7 days post-drug, then this would suggest a fully powered study is warranted using the 0.5mg/kg PO dose.

If the 0.5mg/kg IM dose of ketamine is well-tolerated (i.e., zero treatment-related SAEs) and demonstrates mean clinical improvement in demoralization assessed by DS-II that endures beyond 7 days post-drug, then this would suggest a fully powered study is warranted using the 0.5mg/kg IM dose.

If the either dose is well-tolerated and fails to demonstrate mean clinical improvement in demoralization assessed by DS-II that endures beyond 7 days post-drug, then this would suggest that the dose is an appropriate control for other psychoactive investigational drugs whose clinical effects are expected to have greater durability.

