Study Description	This is a single-site, parallel-arm double-blind randomized controlled pilot trial (N=12) of 0.5mg/kg oral ketamine vs. 0.5mg/kg intramuscular ketamine, each administered as a single dose, in combination with 4 sessions of Meaning and Purpose therapy (MaP), for adults diagnosed with stage 3 or 4 gastrointestinal (GI) cancers (i.e., primary pancreatic, colorectal, hepatocellular, biliary, and gastro-esophageal cancers) who have moderate-to-severe demoralization. The combination of ketamine and Meaning and Purpose therapy will be referred to as K-MaP.			
MaP is a brief, existential behavioral intervention. It is a form of talk therapy designed to help patients cope with demoralization through review of the patient's value and worth, their key relationships, and sources of fulfillment and meaning in life [1]. Participants will have sessions of MaP before drug administration, and 2 sessions after administration. The expected study duration from enrollment to stu completion is up to 63 days for each participant.				
	Demoralization is a clinically significant and measurable form of existential distress characterized by poor coping and a sense of helplessness, hopelessness, and a loss of meaning and purpose in life [2, 3]. Demoralization will be measured by Demoralization Scale-II (DS-II), a validated measure [4]. The scale includes 16 items, the total score range is 0-32, and a score of 10 or higher indicates moderate-to-severe demoralization [4, 5]. DS-II will be assessed at baseline, after 2 sessions of MaP but before ketamine, and then 1, 2, and 5 weeks after ketamine. A change in the DS-II of at least 2 points has been considered clinically meaningful in palliative care patients and will be used as a minimum point reduction indicative of efficacy [4].			
Phase of Study	Pilot			
Investigational Products Ketamine				
Study population	Adult stage 3 and 4 GI cancer patients with moderate to severe demoralization.			
Primary Objective	To assess the feasibility of Meaning and Purpose therapy combined with ketamine (K-MaP) in demoralized patients.			

Pilot Study - Ketamine Page 3 of 55

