Secondary Objectives	 To characterize the preliminary safety and tolerability of K-MaP in demoralized patients with stage 3 and 4 GI cancers. To assess the magnitude and durability of improvement from randomization in psychosocial distress. To assess the magnitude and durability of improvement from randomization in pain. To assess the magnitude of change from randomization in opioid analgesic use. To assess the magnitude and durability of change from randomization in interoceptive awareness. 							
Sample Size	12 patients, 6 patients per arm. Arm A: (0.5 mg/kg of ketamine, PO) Arm B: (0.5 mg/kg of ketamine, IM)							
Duration of Study Treatment	Ketamine will be given once on Day 0/Visit 4. Patients will receive MaP therapy 4 times, twice before ketamine administration (Day 0), and twice afterward: 1. Day -13 to -4/Visit 2 2. Day -12 to -1/Visit 3 3. Day 3 (+/- 2 days)/Visit 5 4. Day 11 (+/-2 days)/Visit 7 The duration of treatment for K-MaP therapy (ketamine and MaP) is approximately up to 28 days.							
Duration of Follow up	Patients will be followed up to 35 days (+/-2 days) after ketamine administration.							

Pilot Study - Ketamine Page 4 of 55

Study Schema

Pilot Study - Ketamine Page 5 of 55

List of Abbreviations

AE adverse event

ALP alkaline phosphatase

ALT alanine aminotransferase
AST aspartate aminotransferase

BMP Basic Metabolic Panel

BPI-SF Brief Pain Inventory-Short Form

BUN blood urea nitrogen

CBC complete blood cell (count)

CEQ Challenging Experience Questionnaire

CMP Comprehensive Metabolic Panel

CNS central nervous system

CR complete response

CRF case report form

C-SSRS Columbia Suicidality Severity Rating Scale

CT computerized tomography

CTCAE Common Terminology Criteria for Adverse Events

CTMS Clinical Trial Management System

DFS disease-free survival
DLT Dose-limiting toxicity
DS-II Demoralization Scale II

DSMC Data and Safety Monitoring Committee

DSMP Data and Safety Monitoring Plan

ECG/EKG electrocardiogram

ECOG Eastern Cooperative Oncology Group

FACIT- Functional Assessment of Chronic Illness Therapy Palliative Care 14 Item Version

Pal-14

FDA Food and Drug Administration

FDG Fluorodeoxyglucose

GAD7 General Anxiety Disorder-7

GCP Good Clinical Practice
GFR glomerular filtration rate

HBsAb hepatitis B surface antibody HBsAg hepatitis B surface antigen HBcAb hepatitis B core antibody

HC Ab hepatitis C antibody

Pilot Study - Ketamine Page 6 of 55

List of Abbreviations

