We will test two different doses and routes of ketamine administration: 0.5mg/kg PO and 0.5mg/kg IM. These doses were selected on the basis of existing data. As a safety precaution, we will use a maximum limit of oral ketamine of 60 mg, given that higher doses have not been evaluated in clinical trial settings in the U.S.

Case series and one published clinical trial of oral ketamine as a treatment of depression in patients with advanced cancer have shown that a daily oral dose of 0.5mg/kg is well-tolerated and briefly improved depression symptoms [55-57]. An ongoing trial of weekly oral ketamine for anxiety in patients with pancreatic ductal adenocarcinoma (PDAC) is using a dose of 0.5mg/kg PO [58]. The bioavailability of oral ketamine is estimated to be 10-17% [59].

Clinical trials investigating the use of intramuscular ketamine for the treatment of depression in palliative populations and the general public have used starting doses ranging from 0.1mg/kg -1.0mg/kg IM [60-62], all of which have been reported to be relatively well-tolerated. The bioavailability of intramuscular ketamine is 93% [63, 64]. Similar or higher doses of ketamine are frequently used in various clinical settings. Many trials of IV ketamine for unipolar depression have used a dose of 0.5mg/kg administered as a slow infusion [65], while one survey of n=98 community clinics administering off-label ketamine for psychiatric conditions uses doses ranging from 0.5-3.0mg/kg IV [66]. A retrospective study of n=420 patients receiving IM ketamine for depression found starting doses ranging from 0.3 - 2.15mg/kg IM, with a median starting dose of 0.55mg/kg IM [67]. A second case series of n = 40 patients utilized a protocol involving a starting dose of ketamine 1.0mg/kg IM, divided into two 0.5m/kg IM doses spaced 15 minutes apart [68]. In a recent systematic review of ketamine in palliative care populations, patients were most commonly started at starting doses of ketamine 0.5mg/kg SC or IV [69]. Another survey of three ketamine clinics (two of which are in the San Francisco Bay Area) provided data on n=253 patients treated with off-label ketamine-assisted psychotherapy using sublingual administration (with a bioavailability of 15-25%) at doses of 25-400 mg, and often in the range of 200-250 mg [70]. Finally, in an FDA-related abuse liability study published in 2011, 100 mg of oral ketamine was used as a control drug for the serotonin 2C receptor agonist lorcaserin [71].

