K-MaP will consist of 4 sessions of Meaning and Purpose (MaP) therapy and a single dose of ketamine on Day 0. Two MaP sessions will occur prior to ketamine therapy at least 2 days apart, the 1st session between Days -13 and -4, and the second session between Days -12 and -1. The two sessions of MaP after ketamine administration will occur on Days 3 (+/- 2 days) and 11 (+/- 2 days). All five intervention visits will be booked at the participant's baseline visit (see Study Schema).

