9.1.2 Randomization

Participants will be randomized 1:1, without stratification, in block sizes of 4.

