Secondary Objective #2: To assess the magnitude and durability of improvement from randomization in psychosocial distress associated with K-MaP, we will measure mean trends in patient-reported outcomes (DS-II, PHQ9, GAD7, FACIT-PAL-14 scores) in each study arm from baseline visit (Day -28 to -7) to post-ketamine (on Days 7, 14, and 35). In addition, we will calculate the proportion of participants per arm who no longer meet criteria for moderate-to-severe demoralization (i.e., DS-II > 10) post-ketamine. We will also measure mean trends in clinician-rated outcomes (CGI-S, DI, and GRID-HAMD-6 scores) per arm as above. ANCOVA models of follow-up endpoints as a function of study arm, adjusted for endpoints at baseline and randomization, will be conducted [110]. ANCOVA results will be presented graphically via mean trends per arm overlaid on individual trends, and via the mean (95% CI) difference between arms at Day 35. Cohen's d will be calculated at each follow-up time to estimate effect sizes. Any missing data will be estimated through the use of single imputation with baseline observations carried forward.

Secondary Objective #3: We will evaluate BPI-SF scores analogously to DS-II scores.

Secondary Objective #4: We will evaluate opioid analgesia use analogously to DS-II scores.

Secondary Objective #5: We will be using pair t-tests to measure mean changes in MAIA-2 scores in each study arm from prior to ketamine administration (on Day 0) to post-ketamine (on Day 7).

Secondary Objective #6: To assess how participants' subjective experiences with ketamine may be related to clinical outcomes, subjective reports of each participant's ketamine experience (videorecorded from Day 0) will be transcribed, inductively coded, and qualitatively analyzed to identify phenomenological content. In addition, participant MEQ and CEQ scores, which provide summary measures of the intensity of ketamine's acute effects, will be evaluated for potential correlation with trends in DS-II, BPI-SF, and opioid use.

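### Section 9.1.1 bases a dose-specific progression statement on uncontrolled within-arm DS-II change, so it cannot separate the ketamine dose from MaP, expectancy or time

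*Combined protocol and SAP*

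**What the plan says.** Section 9.1.1 applies one rule to each arm separately. The arm must have no treatment-related SAE and must show "mean clinical improvement in demoralization assessed by DS-II that endures beyond 7 days post-drug, then this would suggest a fully powered study is warranted", and the sentence ends by naming that arm's dose and route. A third branch takes a well-tolerated dose without lasting improvement and calls it a suitable control for other psychoactive drugs. No between-arm difference and no MaP-only reference enters any branch.

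The rest of the plan supplies the context:

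- The Abstract gives "12 patients, 6 patients per arm", with ketamine in both arms. Of a 2-point fall in DS-II it says that it "will be used as a minimum point reduction indicative of efficacy". Section 9.1.1 does not repeat this threshold.
- Section 3.1: "The two sessions of MaP after ketamine administration will occur on Days 3 (+/- 2 days) and 11 (+/- 2 days"). This applies to both arms.
- DS-II after dosing is taken on Days 7, 14 and 35 (Section 6.1), so only Days 14 and 35 lie beyond 7 days.
- Section 9.2.3, Secondary Objective #2: "ANCOVA models of follow-up endpoints as a function of study arm, adjusted for endpoints at baseline and randomization, will be conducted", with a mean difference and 95% CI between arms at Day 35. Section 9.1.1 does not refer to this estimate.

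**The concern.** Whatever moves both arms alike counts towards a pass in each: response to MaP, the expectation of receiving ketamine (which every participant will receive), or the course of distress over five weeks. Both post-dose MaP sessions normally come before the two scores that can decide the rule. If change is taken from the baseline visit, as the mean trends in Section 9.2.3 are, all four MaP sessions fall inside it.

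The text then assigns the result to a dose. The same shared change affects the third branch: a dose that adds nothing to MaP would not be recognised as a control if its arm improved through MaP. At stake is the stated basis for the next trial, since this is the only progression statement that names a dose. The feasibility and safety aims are not affected.

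**Working it through.** **Figures in the plan.** No alpha, power, effect size or SD lies behind N = 12, so there is no power figure to reproduce. The accrual arithmetic agrees: 24 screened × 50% eligible = 12.

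**Inputs.**
- From the documents: n = 6 per arm; threshold 2 points (Abstract); deciding visits Days 14 and 35.
- Assumed, because the documents do not give them: SD of DS-II change s = 4, 5 or 6; correlation 0.6 between the Day 14 and Day 35 changes; shared non-drug improvement (drift) m = 0, 1 or 2 points. The ketamine effect is set to zero, and the no-related-SAE condition is taken as met.

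**Plausible drift.** The only MaP-alone figure in the documents is in Section 1.1: a pre-post d of 0.16 (95% CI -0.29 to 0.86) after six sessions in 45 patients not selected for distress. If d is scaled on the SD of change, it corresponds to 0.16 × 4 = 0.6 up to 0.16 × 6 = 1.0 point. The upper limit corresponds to 0.86 × 4 = 3.4 up to 0.86 × 6 = 5.2 points. A drift near 1 point matches the estimate, and 2 points is not excluded.

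**One visit (Day 14).** P(pass) = 1 - Φ((2 - m)/(s/√6)). For s = 5 the SE is 5/√6 = 2.04, so:
- m = 0: 1 - Φ(0.98) = 0.16
- m = 1: 1 - Φ(0.49) = 0.31
- m = 2: 1 - Φ(0) = 0.50

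**Both visits (Days 14 and 35).** P(pass) is the bivariate normal probability, with correlation 0.6, that both arm means reach 2 points. For s = 5 it is 0.08, 0.18 and 0.35 at m = 0, 1 and 2.

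| Shared drift | One arm, 2 points at Day 14 (SD 4-6) | One arm, 2 points at both visits (SD 4-6) |
|---|---|---|
| 0 | 11-21% | 4-10% |
| 1 point | 27-34% | 15-21% |
| 2 points | 50% | about 35% |

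**At least one of two inert doses passes:** 1 - (1 - p)². At s = 5 and m = 1 this is 1 - 0.69² = 52% on the Day 14 reading and 1 - 0.82² = 33% on the both-visits reading.

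**What the randomized contrast could add.** With 6 per arm, the 95% CI half-width for IM minus PO is 2.228 × s × √(2/6), which is 5.1, 6.4 and 7.7 points for SD 4, 5 and 6 (unadjusted, 10 df). The contrast removes drift common to both arms, but it also removes any ketamine benefit common to both. Section 1.3 says "The bioavailability of oral ketamine is estimated to be 10-17" percent, against 93% for IM. The arms thus differ in exposure by a factor of about 93/17 = 5.5 to 93/10 = 9.3, and neither is drug-free.

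**The case against.** The strongest defence is that the rule claims little. Section 9.1.1 opens with "No formal power analysis was conducted, and no formal tests of efficacy will be conducted", a positive arm only suggests a later study, and the hypothesis and Secondary Objective #2 concern K-MaP as a combination. Naming the dose can be read as saying which dose to carry forward within the package. A false pass leads to another trial, where the drug's contribution could be tested. This limits the harm, but the sentence still names a dose, and the third branch classifies the dose itself.

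The size also rests on assumed drift and SD. The MaP-alone estimate is small, the repeated DS-II screen of 10 or more limits regression to the mean, and carrying baseline forward for missing scores generally pulls change towards zero. All of this stands, and it is why the result is given as a range.

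A reader might infer that an inert dose passes half the time, or 1 - 0.5² = 75% of the time for at least one arm, even with no drift. Those figures need any mean improvement to count, which sets aside the Abstract's 2-point minimum. They also reflect sampling noise at n = 6, not MaP.

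A reader might also conclude that the IM-PO difference should become a condition for progression. The design does not support that. Suppose both doses truly gave 4 points, and the IM statement required 2 points in its own arm plus a 2-point advantage over PO at Day 14. It would then pass only 19-28% of the time at SD 4-6.

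**Conclusion.** The concern holds as one of attribution. Section 9.1.1 turns an uncontrolled within-arm change into a statement about a dose, and the design cannot separate that dose from MaP, expectancy or time. With the 2-point minimum and no ketamine effect, one arm passes in 11-50% of trials on Day 14 alone and in 4-35% if both visits are required, as drift goes from 0 to 2 points. These rates rest on the assumed SD, correlation and drift. Taking the SAE condition as met makes them upper bounds in that respect.

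Two stronger readings are not supported. The documents do not show that the rule will recommend an inert dose; they show only that it could not detect one. Nor do they show that the randomized comparison is ignored, because Section 9.2.3 estimates it and reports its interval. It is simply not linked to 9.1.1, and at 6 per arm it is too imprecise to decide progression. Similar improvement in both arms would neither show nor exclude a ketamine effect.

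**What to change.** Reword Section 9.1.1:

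1. An arm that meets the criteria suggests that a fully powered controlled study of K-MaP as given in that arm is warranted. Add that this pilot does not identify the contribution of ketamine.
2. Limit the third branch in the same way: the arm's result describes the package and does not by itself classify the dose as a control.
3. Beside these statements, report the IM-PO ANCOVA difference already planned in Section 9.2.3, with its 95% CI at Day 35 and optionally at Day 14. Label it as descriptive and not a condition for progression, and note that similar improvement in both arms neither shows nor excludes a ketamine effect.

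This takes a few sentences and at most one extra reported interval, with no new patients, visits or data. The price is a weaker claim about dose.

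### Section 9.1.1 reads a tolerated six-patient arm's failure to show lasting DS-II improvement as support for using that dose as a control, and allows no inconclusive result

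*Combined protocol and SAP*

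**What the plan says.** The abstract gives the sample size as "12 patients, 6 patients per arm". Section 9.1.2 confirms 1:1 allocation. Section 9.1.1 states: "No formal power analysis was conducted, and no formal tests of efficacy will be conducted".

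Section 9.1.1 then sets out three conclusions, each conditional on the dose being well tolerated, which the first two define as zero treatment-related SAEs:

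- Two are positive. If the oral arm, or the intramuscular arm, shows mean clinical improvement on the DS-II beyond 7 days, a fully powered study of that dose is suggested.
- The third is negative. Its condition is that a tolerated arm, oral or intramuscular, "fails to demonstrate mean clinical improvement in demoralization assessed by DS-II that endures beyond 7 days post-drug". The inference drawn in that case reads: "this would suggest that the dose is an appropriate control for other psychoactive investigational drugs". The sentence goes on to limit this to drugs whose effects are expected to last longer.

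Section 9.1.1 gives no number for clinical improvement. The abstract does: "A change in the DS-II of at least 2 points has been considered clinically meaningful in palliative care patients", and this change "will be used as a minimum point reduction indicative of efficacy". The DS-II is scored so that "the total score range is 0-32".

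Section 9.2.3 places follow-up DS-II assessments at Days 7, 14 and 35. It plans Cohen's d at each follow-up, individual trends, and one 95% CI, for the difference between arms at Day 35. Missing data are filled in by carrying the baseline value forward.

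**The concern.** The third conclusion turns a failure to demonstrate something in six people into a positive statement about the dose. To call a dose suitable as a control for longer-acting drugs, one needs evidence that its lasting effect is small. That requires an upper bound on the effect, and a point estimate below a bar does not give one.

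For a tolerated dose the rule has two exits: a fully powered study, or a control role. It has no confidence interval, no margin and no inconclusive zone. The one planned interval compares the arms with each other, so it cannot show that either arm lacks benefit.

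The stake is the design of a later trial. If a dose with a real lasting effect were taken forward as the comparator, it would shrink the contrast in the very durability comparison it was chosen for, and cost that trial power.

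**Working it through.** **What the plan gives.** There is no stated error rate, power or SD to reproduce. The arithmetic that can be checked is 12/2 = 6 patients per arm.

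**Inputs**
- n = 6 per arm (abstract, sample size).
- Bar for improvement: 2 points (abstract). Section 9.1.1 does not restate it, so a bar of 0 is also tried.
- SD of change: not in the documents. Assumed 4, 5 and 6 points on the 0-32 scale.
- One deciding visit, complete data, and a dose that meets the tolerability condition.

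**Step 1. Standard error of an arm mean:** SD/√6 = 1.63, 2.04 and 2.45 for SD 4, 5 and 6.

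**Step 2. Chance that the observed mean misses the bar**, for a true lasting fall μ: Φ((bar − μ)/(SD/√6)). For example, with bar 2, μ = 3 and SD 4: Φ(−1/1.63) = Φ(−0.612) = 0.270.

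| Bar | True fall | SD 4 | SD 5 | SD 6 |
|---|---|---|---|---|
| 2 | 2 | 50% | 50% | 50% |
| 2 | 3 | 27% | 31% | 34% |
| 2 | 4 | 11% | 16% | 21% |
| 0 | 2 | 11% | 16% | 21% |
| 0 | 3 | 3% | 7% | 11% |
| 0 | 4 | 1% | 3% | 5% |

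**Step 3. Precision of an arm mean.** The 95% CI half-width is t(0.975, 5 df) × SD/√6 = 2.571 × (1.63, 2.04, 2.45) = 4.2, 5.25 and 6.3 points. If the observed mean change were exactly 0, the upper limit would still be 4.2 to 6.3 points of improvement, well above 2.

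**Step 4. How often six patients could support the control conclusion.** Require the upper 95% limit to be below 2 points when the true change is 0. With the sample SD allowed to vary, this is a noncentral t probability with 5 df and noncentrality −2/(SD/√6), evaluated at −2.571. The results are 17%, 12% and 10% for SD 4, 5 and 6.

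**Step 5. Features that add to the risk**
- *Deciding visit.* The text does not say whether Day 14, Day 35 or both settle the words on lasting beyond 7 days. If both must reach 2 points, with an assumed correlation of 0.7, the miss rate for a true 3-point fall at SD 5 rises from 31% to 42%.
- *Missing data.* If change is measured from the baseline visit, carrying baseline forward gives a missing patient zero improvement. With 1 of 6 missing, a true 3-point fall and SD 5: Φ((2 − 3 × 5/6)/(5 × √5/6)) = Φ(−0.5/1.86) = 39%.

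**The case against.** The strongest reply is that this is a feasibility pilot that disclaims efficacy testing. All three conclusions are worded as suggestions, and nothing commits a later trial to this comparator. That is fair and lowers the consequence. It does not supply the missing inconclusive outcome.

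A reader might infer that the plan would label an active dose as inactive or use it as an inert control. The documents do not support this. Section 9.1.1 never calls the dose inactive, and it confines the control role to drugs expected to have more durable effects. A dose with acute or short-lived effects fits that role. What can go wrong is narrower: a durably active dose may be described as lacking a durable effect. For the same reason the harm to a later trial is a smaller contrast. It would be bias only if the comparator were presented as inert.

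A reader might also infer that the rule has only two outcomes in every case. A dose with a treatment-related SAE receives neither label, so the two-exit description applies to tolerated doses only.

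Two points about size also stand. The 2-point bar is carried over from the abstract, and if any improvement counts, the error rates fall sharply. It would also be too strong to say that the design can almost never support a control conclusion: on the assumed SDs it could do so in about one trial in ten to one in six when the true change is 0.

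Finally, Section 9.2.3 does plan effect sizes and individual trends. They help a reader, but none is tied to the rule, and the between-arm interval answers a different question.

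**Conclusion.** The concern holds in this form: for a tolerated dose, Section 9.1.1 draws a positive suggestion about suitability as a control from a six-patient arm mean that falls short, with no interval and no inconclusive result. Nothing elsewhere in the plan repairs this.

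With an assumed SD of 4 to 6 and a 2-point bar, the control label would be wrongly applied in 27% to 34% of trials for a true lasting 3-point fall, and in 11% to 21% for a 4-point fall. With a bar of 0 the ranges are 3% to 11% and 1% to 5%. The logical fault does not depend on the SD or the bar; the size does. The correction should be made because it is cheap. It does not threaten the feasibility objective.

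**What to change.** In Section 9.1.1:

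1. Name the visit or visits (Day 14, Day 35 or both) that decide whether improvement lasted beyond 7 days, and state that the 2-point bar of the abstract applies.
2. Report each arm's mean DS-II change at that visit with its 95% CI beside every go or control statement.
3. Suggest a dose as a candidate control only if that CI excludes a 2-point improvement, meaning that its upper limit is below 2 points. Otherwise state that the result on durable effect is inconclusive.

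This takes a few sentences and needs no new patients, visits or data. The cost is that inconclusive becomes the likely outcome for a non-improving arm: with a true change of 0 the criterion is met in only about 10% to 17% of trials at SD 6 to 4. Meeting it with 80% probability would take about ((1.96 + 0.84) × 5/2)² ≈ 50 patients per arm at SD 5 (normal approximation; 18 at SD 3, 97 at SD 7). That is no reason to enlarge the pilot. It shows how little six patients per arm can say about the absence of a lasting effect.
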